6.2.7 Inexact Values

In the case where a variable is recorded as “ $> x$ ”, “ $\geq x$ ”, “ $< x$ ” or “ $\leq x$ ”, a value of x will be taken for analysis purposes.

6.2.8 Columbia-Suicide Severity Rating Scale

The following outcomes are C-SSRS categories and have binary responses (yes/no). The categories have been re-ordered from the actual scale to facilitate the definition of composite endpoints:

Category 1	Wish to be Dead
Category 2	Non-specific Active Suicidal Thoughts
Category 3	Active Suicidal Ideation with Any Methods (Not Plan) without Intent to Act

Category 4	Active Suicidal Ideation with Some Intent to Act, without Specific Plan
Category 5	Active Suicidal Ideation with Specific Plan and Intent
Category 6	Preparatory Acts or Behavior
Category 7	Aborted Attempt
Category 8	Interrupted Attempt
Category 9	Actual Attempt (non-fatal)
Category 10	Suicidal Behavior (Baseline/Screening version) / Suicide (Since Last Visit version)

Suicidal Ideation at baseline – A “yes” answer at baseline (Screening visit) to any one of the 5 suicidal ideation questions (categories 1-5) for Lifetime or Past 6 Months on the C-SSRS Baseline/Screening version

Suicidal Behavior at baseline – A “yes” answer at baseline (Screening visit) to any one of the 5 suicidal behavior questions (categories 6-10) for Lifetime or Past 6 Months on the C-SSRS Baseline/Screening version

Suicidal Ideation since baseline – A “yes” answer at any time during double blind treatment to any one of the 5 suicidal ideation questions (categories 1-5) on the C-SSRS Since Last Visit version

Suicidal Behavior since baseline – A “yes” answer at any time during double blind treatment to any one of the 5 suicidal behavior questions (categories 6-10) on the C-SSRS Since Last Visit version

There will be no imputation of missing data for C-SSRS.

[figure not shown]

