6.12.8 C-SSRS

C-SSRS will be used to assess suicidal ideations and behaviors. Number of subjects that responded 'yes' to any of the C-SSRS Suicidal Ideation Items, as described in Section [6.2.8](#), will be presented by treatment group, and will be tabulated separately for screening and post-screening assessments. Similarly, number of subjects that responded 'yes' to any of the C-SSRS Suicidal Behavioral Items, as described in Section [6.2.8](#), will be presented by treatment group, and will be tabulated separately at screening and post-screening assessments. For subjects that were randomized under earlier versions of the protocol, that is, prior to addition of the C-SSRS on the study assessments, the screening version of the C-SSRS that were completed at the visit at which they are currently in when they signed the informed consent for the new version of the protocol (v4.0 dated 15-JUL-2019) will be not be tabulated but will be listed. Derived C-SSRS data as described in Section [6.2.8](#) will be listed for screening and post-screening assessments for all subjects.

[figure not shown]

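### The C-SSRS baseline is a lifetime any-yes and is tabulated apart from the post-screening any-yes, so the visible tables generally cannot separate new from long-standing suicidality and never show worsening within ideation

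*SAP*

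**What the plan says.** SAP 6.2.8 orders the C-SSRS into ten yes/no categories, 1-5 for ideation and 6-10 for behavior. Baseline is tied to the Screening visit. Ideation is present on any yes, "categories 1-5) for Lifetime or Past 6 Months on the C-SSRS Baseline/Screening version", and behavior on any yes, "categories 6-10) for Lifetime or Past 6 Months on the C-SSRS Baseline/Screening version". Ideation since baseline is a yes "answer at any time during double blind treatment to any one of the 5 suicidal ideation questions (categories 1-5") on the Since Last Visit version, with no reference to what the subject reported before. Behavior since baseline is defined in parallel.

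SAP 6.12.8 gives the tabulated statistic for ideation as "Number of subjects that responded 'yes' to any of the C-SSRS Suicidal Ideation Items". This is shown by treatment group and "will be tabulated separately for screening and post-screening assessments", with behavior handled alike. Derived data "will be listed for screening and post-screening assessments for all subjects". For subjects randomized before the scale was introduced, the screening form they completed late "will be not be tabulated but will be listed".

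Three other places matter. Protocol 12.3.9 describes the scale as a monitor of change over time. Protocol 12.1.3 has a Since Last Visit form completed on Day 1 before treatment. SAP 6.12.2 and 6.12.4 plan baseline-to-post shift tables for laboratory and ECG data.

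**The concern.** The scale is in the trial to detect change after injection, but no C-SSRS summary in the visible text measures change within a subject. Three features combine:

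- The baseline flag uses the longest recall window on the form, so the recent-window answer has no effect on it.
- The screening and post-screening counts are separate totals, not linked within subject.
- Ideation categories 1-5 are pooled. A subject who moves from a wish to be dead (category 1) to a plan with intent (category 5) is one yes before and one yes after.

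At stake is a prespecified by-arm count of emergent or worsened suicidality. Without it, that count has to be assembled from listings after the fact, and the two tables invite a before-after reading across windows of very different length.

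**Working it through.** The documents give no C-SSRS rate or count, so there is no figure to reproduce. Four checks follow.

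**1. The baseline rule.** Let L be a lifetime yes and R a past-six-months yes. If the form is answered consistently, R is contained in L, so (L or R) = L. Two subjects with the same lifetime answer and different recent answers receive the same baseline flag.

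**2. What separate totals reveal about new onset.** Take n subjects in both tables, a with yes at screening and b with yes afterwards. The number with yes only afterwards lies between max(0, b − a) and min(b, n − a). Allocation is not visible, so n = 50 per arm (about 150 subjects in three equal arms) is an assumption.

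| Screening yes (a) | Post yes (b) | Lower bound | Upper bound |
|---|---|---|---|
| 6 | 3 | max(0, −3) = 0 | min(3, 44) = 3 |
| 3 | 3 | max(0, 0) = 0 | min(3, 47) = 3 |
| 2 | 4 | max(0, 2) = 2 | min(4, 48) = 4 |
| 0 | 2 | max(0, 2) = 2 | min(2, 50) = 2 |

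The totals fix the answer when nobody in the arm is positive at screening, and narrow it when b exceeds a. Otherwise they leave it open. A cross-tabulation of the same subjects gives the exact number. No pair (a, b) says anything about a move between categories 1 and 5.

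**3. Direction and size of the before-after contrast.** The screening count covers a lifetime (at least 18 years, by the age criterion). The post-screening count covers about 24 weeks, or about 8 for early study completers. The longer window collects more yes answers with no drug effect.

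To see how much, assume lifetime prevalence π, post-screening yes risk r1 with a history and r0 without, and n = 50. Expected counts are 50π at screening and 50[π·r1 + (1 − π)·r0] afterwards. A fall occurs when subjects who are yes then no (probability π(1 − r1)) outnumber those who are no then yes (probability (1 − π)r0), computed from the exact trinomial. The one-arm probability is cubed for three arms. The middle columns use r1 = 0.1 and r0 = 0.01. The last column is the range over (r1, r0) = (0.1, 0), (0.1, 0.01) and (0.2, 0.02).

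| π | Expected screening | Expected post | P(fall), one arm | P(fall), all three arms | Range, all three arms |
|---|---|---|---|---|---|
| 1% | 0.5 | 0.55 | 0.246 | 0.015 | 0.3-5% |
| 2% | 1.0 | 0.59 | 0.439 | 0.085 | 2-21% |
| 5% | 2.5 | 0.73 | 0.784 | 0.481 | 24-73% |
| 10% | 5.0 | 0.95 | 0.963 | 0.893 | 71-97% |
| 15% | 7.5 | 1.18 | 0.995 | 0.984 | 93-99.8% |

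For example, at π = 10% the expected post count is 50 × (0.10 × 0.1 + 0.90 × 0.01) = 0.95, and 0.963³ = 0.893. All π, r1 and r0 are assumptions.

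**4. Which forms and subjects enter each table.** SAP 6.2.8 limits the post-baseline flag to double-blind treatment, while SAP 6.12.8 tabulates everything after screening. The Day 1 pre-treatment form falls between the two, so answers given before injection may enter the post-screening column. Subjects whose screening form is left out of the table may still appear in the post-screening table, in which case the two tables describe different subjects.

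**The case against.** The strongest reply is that safety inference here rests on randomization, not on a before-after contrast. The lifetime window affects only the screening table, and active arms can still be compared with placebo on the post-screening count. This stands, although that comparison still mixes first-ever with long-standing ideation and hides severity.

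There are also other routes to cases. Derived data are listed for every subject. The investigator reviews the scale at each visit (Protocol 12.3.9). Clinically significant changes in safety evaluations are to be reported as AEs (Protocol 12.3.1.2.1), and SAP 6.12.1 counts worsening of a pre-existing AE as treatment-emergent. This stands too, but neither the listings nor the AE tables give a prespecified by-arm count of emergence on the scale itself.

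The C-SSRS is not named among the safety endpoints in SAP 3.4, and few events are expected. That limits the weight of the point without removing it.

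Parts of the SAP and of the eligibility criteria are blacked out. A further C-SSRS table, or an exclusion that lowers prevalence, cannot be ruled out.

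A reader might infer two stronger things. One is that the tables will show a fall in every arm. The documents give no prevalence, and the calculation makes that outcome likely only at about 10% lifetime prevalence or more. Leaving some screening forms untabulated also pulls the other way. The other is that the tables cannot show new cases at all. They can when an arm has no yes at screening and both tables cover the same subjects.

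**Conclusion.** The point holds as a gap in safety reporting and does not touch the primary endpoint. On the visible text, the baseline flag is lifetime history, the separate any-yes totals generally leave new onset undetermined (0 to 3 of 3 post-screening cases in the first example), and worsening within categories 1-5 is never visible. Reading screening against post-screening is biased toward an apparent fall because the windows differ, but the size of that bias cannot be stated from the documents. The new-onset examples assume 50 subjects per arm present in both tables. The fall probabilities also rest on the assumed prevalences and risks.

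**What to change.** In SAP 6.2.8, derive recent baseline as the worst answer across the past-six-months items at Screening and the pre-dose Day 1 Since Last Visit form. Report lifetime as a separate history row.

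In SAP 6.12.8:

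- Restrict the post-baseline column to post-dose assessments, which also reconciles it with 6.2.8.
- Add a by-arm shift table of worst category before versus after dosing, with counts of new-onset subjects (none before, any after) and worsened subjects (higher category after than before).
- Do this separately for ideation (categories 1-5) and behavior (categories 6-9). Report category 10 on its own, because it means suicidal behavior on the Baseline/Screening version and suicide on the Since Last Visit version. In a combined ranking, a subject positive on it at baseline could never count as worse.
- State the denominator as subjects with a pre-dose C-SSRS, and show subjects randomized before the scale was added separately.

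SAP 6.2.8 shows that both recall windows are on the form, and the Day 1 form is already scheduled, so no new data are needed. The cost is revised wording in two sections and one extra safety table with small counts.

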6.2.9 Early Withdrawal Assessments

For the analysis, assessments performed at early withdrawal visits for the subjects who discontinued will be assigned to the next scheduled visit the assessment was scheduled to be assessed. For early study completers, the assessments for Week 24/ET visit will be remapped back to Week 8.

6.2.10 Unscheduled Visits

Only scheduled post-baseline vital signs, ECG values, and foot and ankle examination will be tabulated. Post-baseline repeat/unscheduled assessments will be disregarded, although these post-baseline assessments will be listed in the relevant appendices to the CSR. For laboratory assessments, if a repeat assessment is available, this will be tabulated instead of the scheduled assessment. Post-baseline unscheduled assessments that were not a repeat for a scheduled assessment will be disregarded but will be listed in the relevant appendices to the CSR.

6.2.12 Change from Baseline

Change from baseline in absolute terms is defined as the baseline value subtracted from the post-baseline value. This calculation method will be used as part of the calculation for percentage change from baseline calculations.

[figure not shown]
6.2.13 Percent Change from Baseline

Percent change from baseline will be calculated as change from baseline multiplied by 100 then divided by the baseline value.

6.3 Conventions

All data listings, summaries, figures and statistical analyses will be generated using SAS version 9.4 or higher¹.

6.3.1 Decimal Places

Decimal places for derived data described in section 6.2 will be determined by the scale of measurement unless otherwise stated. No decimal places will be displayed if the smallest calculated value is ≥ 100 ; 1 decimal place will be displayed when the smallest value is within the interval (10, 100), with 10 being inclusive; 2 decimal places will be displayed when the smallest value is within (1, 10), with 1 being inclusive; and so on for even smaller scales of measurement.

Derived data where it is known in advance the result will be an integer, for example number of days or total score, will be presented with zero decimal places.

Means, medians and quartiles will be displayed to one more decimal place than the data, dispersion statistics (e.g. standard deviation) will have two more decimal places, and the minimum and maximum will be displayed to the same number of decimal places as reported in the raw data. Percentages will be displayed with one decimal place.

P-values will be quoted to 4 decimal places. P-values < 0.0001 will be presented as $p<0.0001$.

6.4 Subject Disposition

Subject disposition will be summarized as follows:

- The number of subjects randomized, and number of subjects in each analysis population (Safety, ITT, and PP) will be summarized by treatment group and overall based on all randomized subjects.
- The number of early withdrawals and the reasons for withdrawals will be tabulated by treatment group and overall for the Safety Population.
- The number of subjects who are Week 8 Early Study Completers and Week 24 Study Completers will be summarized by treatment group and overall for the Safety Population.

6.5 Protocol Deviations

Protocol deviations will be classified as Major, Minor and by Criticality. Additionally, any COVID-19-related protocol deviations will be identified. Protocol deviation categories will be

tabulated by treatment group and classification for the Safety Population. The number of subjects impacted by COVID-19, that is, with any COVID-19-related protocol deviation, number of subjects with missed visits, delayed visits, with visits performed remotely, and with missed assessments will be summarized by treatment group for the Safety Population. A listing of critical and major protocol deviations, as well as COVID-19 related protocol deviations will be provided within Appendix 16.2 of the CSR.

6.6 Baseline Comparability

The comparability of treatment groups with respect to subject demographics and baseline characteristics will be assessed in a descriptive manner, but no formal statistical testing will be performed.

Standard continuous or categorical variable summaries will be presented by treatment group and overall, and by treatment group within each investigator site for age (years), gender, fertility status (for female subjects), ethnicity, race, screening height, weight, and BMI based on the Safety Population.

6.7 Medical History

Separate tabulations of previous and ongoing conditions at screening will be presented by treatment group and overall for the Safety Population. Conditions will be presented by Medical Dictionary of Regulated Activities (MedDRA) v.22.0 primary system organ class and preferred term.

6.8 Prior and Concomitant Medications, and Therapies and Relevant Surgical Procedures

Separate tabulations will be produced for prior and concomitant medications presented by treatment group and overall for the Safety Population. Prior medications are defined as all medications starting before the date of dosing of study drug. Concomitant medications are defined as medications taken on or after the date of dosing of study drug. A medication that started before the date of dosing of study drug but ongoing during the study will be classified as both prior and concomitant. Prior and concomitant medications will be coded using WHO Drug Dictionary (Mar 2019) and will be summarized using Anatomic Therapeutic Chemical (ATC) Level 2.

Any type of rescue medication is not permitted in the study prior to Week 8. However, at Week 8, if the subject has less than 20% reduction from baseline in the NPRS score, a physician-

prescribed physical therapy will be permitted upon subject's request. Prior therapies are defined as all therapies starting before the date of dosing of study drug. Concomitant therapies are defined as therapies that started on or after the date of dosing of study drug. A therapy that started before the date of dosing of study drug but ongoing during the study will be classified as both prior and concomitant. Physician-prescribed therapies will also be classified as concomitant. Number of subjects with prior, concomitant, and physician-prescribed therapies, and with relevant surgical procedures will be presented by treatment group and overall for the Safety Population.

6.9 Exposure to Study Drug

The number of randomized subjects that received injection, foot injected (left or right), and whether or not injection was guided with ultrasound will be summarized by treatment group and overall.

6.10 Treatment Compliance

Study subjects will receive a one-time single treatment, [REDACTED]
[REDACTED] Thus, treatment compliance will not be calculated. However, listing of study drug administration will be provided.

6.11 Efficacy Analyses

All statistical tests will be performed using a two-tailed 5% overall significance level, unless otherwise stated.

For the analysis of NPRS-related endpoints, unless otherwise stated, the following will apply. Baseline NPRS score will be the average over 5 days, that is, 4 days prior to Day 1 visit and on Day 1 visit. A minimum of 3 non-missing NPRS scores out of the 5 days is required for the subject's baseline NPRS score. Post-baseline NPRS scores are to be calculated as the average over 5 days, that is, 4 days prior to study visit and on study visit day. A minimum of 3 non-missing NPRS scores out of the 5 days is required for the subject's post-baseline NPRS score. If there are more than 2 days of missing NPRS scores, the NPRS score for the particular post-baseline visit will be set to missing. Non-missing out-of-window NPRS score, that is, time of assessment is more than 15 minutes after first step out of bed in the morning, within the 5 days will be flagged for sensitivity analysis but will still be considered in the calculation of NPRS scores. If a subject missed/skipped a clinic visit, the post-baseline NPRS score for that particular visit will be calculated as the average over 5 days, that is, 4 days prior to expected visit date and

on the expected visit date. The expected visit date is determined relative to the day of dosing (Day 1). For example, if the missed/skipped visit is Week 4, the expected visit date will be Day 1 visit date + 28 days. In the event that the 4 days leading to the expected visit date overlaps with the previous visit's date, only the NPRS scores on the day after the previous visit's date up to the expected visit date will be used to obtain the post-baseline NPRS score for that particular visit given that there is a minimum of 3 days' worth of NPRS scores. Otherwise, the post-baseline NPRS score for that particular visit will be set to missing. If a subject has more than one valid NPRS score at a given timepoint, the NPRS score corresponding to the assessment that has non-missing response on the question "What time did you get out of bed" will be used. However, if all the assessments at a given timepoint have response on the question "What time did you get out of bed", the NPRS score corresponding to the closest assessment to the target visit date will be used. If the assessments are equidistant from the target visit date, the NPRS score at a later assessment will be used.

6.11.1 Primary Endpoint

[figure not shown]
The primary efficacy endpoint is the change from baseline in the NPRS score, which is recorded within 15 minutes after stepping out of bed in the morning and averaged over 5 days (defined as 4 days prior to study visit and on study visit day) at Week 8.

[figure not shown]
The NPRS is a segmented numeric version of the visual analog scale (VAS) in which a respondent selects a whole number (0–10 integers) that best reflects the intensity of his/her pain. The common format is a horizontal bar or line. Similar to the VAS, the NPRS is anchored by terms describing pain severity extremes with a score of 0 representing "no pain" and a score of 10 representing "worst pain imaginable" or "pain as bad as you can imagine".

A large rectangular area of the page is completely blacked out, indicating that the content has been redacted for confidentiality.

6.11.2 Primary Efficacy Analysis

The primary efficacy endpoint will be analyzed using the ITT population.

A large rectangular area of the page is completely blacked out, indicating that the content has been redacted for confidentiality.

[figure not shown]
6.11.3 Sensitivity Analysis

6.11.3.1 ANCOVA on change from baseline in NPRS score at week 8 – Per Protocol Population

To assess the impact of major protocol violations to study results, the change from baseline in NPRS score at week 8, in which the Week 8 NPRS score is calculated as the average over 5

[figure not shown]
days, that is, 4 days prior to Week 8 visit date and on Week 8 visit date, will be analyzed using the same ANCOVA model in the primary analysis applied on the Per Protocol population.

WORLDWIDE CLINICAL TRIALS
SCIENTIFICALLY MINDED • MEDICALLY DRIVEN

[figure not shown]
Revance Therapeutics, Inc.
1820201
Statistical Analysis Plan
Version 1.0
Issue Date 04-SEP-2020

WORLDWIDE CLINICAL TRIALS
SCIENTIFICALLY MINDED • MEDICALLY DRIVEN

[figure not shown]
Revance Therapeutics, Inc.
1820201
Statistical Analysis Plan
Version 1.0
Issue Date 04-SEP-2020

WORLDWIDE CLINICAL TRIALS
SCIENTIFICALLY MINDED • MEDICALLY DRIVEN

[figure not shown]
Revance Therapeutics, Inc.
1820201
Statistical Analysis Plan
Version 1.0
Issue Date 04-SEP-2020

WORLDWIDE CLINICAL TRIALS
SCIENTIFICALLY MINDED • MEDICALLY DRIVEN

[figure not shown]
Revance Therapeutics, Inc.
1820201
Statistical Analysis Plan
Version 1.0
Issue Date 04-SEP-2020

WORLDWIDE CLINICAL TRIALS
SCIENTIFICALLY MINDED • MEDICALLY DRIVEN

[figure not shown]
Revance Therapeutics, Inc.
1820201
Statistical Analysis Plan
Version 1.0
Issue Date 04-SEP-2020

WORLDWIDE CLINICAL TRIALS
SCIENTIFICALLY MINDED • MEDICALLY DRIVEN

[figure not shown]
Revance Therapeutics, Inc.
1820201
Statistical Analysis Plan
Version 1.0
Issue Date 04-SEP-2020

WORLDWIDE CLINICAL TRIALS
SCIENTIFICALLY MINDED • MEDICALLY DRIVEN

[figure not shown]
Revance Therapeutics, Inc.
1820201
Statistical Analysis Plan
Version 1.0
Issue Date 04-SEP-2020

WORLDWIDE CLINICAL TRIALS
SCIENTIFICALLY MINDED • MEDICALLY DRIVEN

Revance Therapeutics, Inc.
1820201
Statistical Analysis Plan
Version 1.0
Issue Date 04-SEP-2020

[figure not shown]
WORLDWIDE CLINICAL TRIALS
SCIENTIFICALLY MINDED • MEDICALLY DRIVEN

Revance Therapeutics, Inc.
1820201
Statistical Analysis Plan
Version 1.0
Issue Date 04-SEP-2020

WORLDWIDE CLINICAL TRIALS
SCIENTIFICALLY MINDED • MEDICALLY DRIVEN

[figure not shown]
Revance Therapeutics, Inc.
1820201
Statistical Analysis Plan
Version 1.0
Issue Date 04-SEP-2020

WORLDWIDE CLINICAL TRIALS
SCIENTIFICALLY MINDED • MEDICALLY DRIVEN

[figure not shown]
Revance Therapeutics, Inc.
1820201
Statistical Analysis Plan
Version 1.0
Issue Date 04-SEP-2020

WORLDWIDE CLINICAL TRIALS
SCIENTIFICALLY MINDED • MEDICALLY DRIVEN

[figure not shown]
Revance Therapeutics, Inc.
1820201
Statistical Analysis Plan
Version 1.0
Issue Date 04-SEP-2020

WORLDWIDE CLINICAL TRIALS
SCIENTIFICALLY MINDED • MEDICALLY DRIVEN

[figure not shown]
Revance Therapeutics, Inc.
1820201
Statistical Analysis Plan
Version 1.0
Issue Date 04-SEP-2020

WORLDWIDE CLINICAL TRIALS
SCIENTIFICALLY MINDED • MEDICALLY DRIVEN

[figure not shown]
Revance Therapeutics, Inc.
1820201
Statistical Analysis Plan
Version 1.0
Issue Date 04-SEP-2020

[figure not shown]

WORLDWIDE CLINICAL TRIALS
SCIENTIFICALLY MINDED • MEDICALLY DRIVEN

Revance Therapeutics, Inc.
1820201
Statistical Analysis Plan
Version 1.0
Issue Date 04-SEP-2020

